Adverse events encompass clinical, physical and psychological harms. Adverse events occur most commonly in the context of biomedical research, although on occasion, they can occur in the context of social and behavioral research. Adverse events may be expected or unexpected.

Acute Adverse Events

Adverse events occurring in the time period from the signing of the informed consent, through 30 days post treatment will be considered acute adverse events.

Late Adverse Events (as applicable)

Adverse events occurring in the time period from the end of acute monitoring, to 2 years post treatment, will be defined as late adverse events. Only Radiation Oncology visits will be reviewed for adverse events.

Severity

Adverse events will be graded by a numerical score according to the defined NCI Common Terminology Criteria for Adverse Events (NCI CTCAE) Version 4.0. Adverse events not specifically defined in the NCI CTCAE will be scored on the Adverse Event log according to the general guidelines provided by the NCI CTCAE and as outlined below.

- Grade 1: Mild
- Grade 2: Moderate
- Grade 3: Severe or medically significant but not immediately life threatening
- Grade 4: Life threatening consequences
- Grade 5: Death related to the adverse event

Serious Adverse Events

ICH Guideline E2A and the UTSW IRB define serious adverse events as those events, occurring at any dose, which meets any of the following criteria:

- Results in death
- Immediately life-threatening
- Results in inpatient hospitalization^{1,2} or prolongation of existing hospitalization
- Results in persistent or significant disability/incapacity
- Results in a congenital anomaly/birth defect
- Based upon appropriate medical judgment, may jeopardize the subject's health and may require medical or surgical intervention to prevent one of the other outcomes listed in this definition.

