10.0 Data Collection

Patient, treatment, HRQOL, and patient perspective costs data (Appendix VII) should be submitted to:

Department of Radiation Oncology
Clinical Research Office
The University of Texas Southwestern Medical Center
Attention: [name], Project Manager
[name]
[name]
[contact]

Economic data (patient bills, and other cost documents) will be collected by:

Department of Epidemiology and Biostatistics School of Rural Public Health Texas A&M Health Science Center, [name]

Attn: [name] [name] [name]

Patients will be identified only by initials (first middle last) and a unique study ID number assigned to each study participant; if there is no middle initial, a hyphen will be used (first-last). Last names with apostrophes will be identified by the first letter of the last name. Identifiable information will be released to Drs. [name] and [name] at Department of Epidemiology and Biostatistics, Texas A&M Health Science Center (TAMHSC) for obtaining the bills that are associated with each service reported in the case report forms.

Item	Due
Demographics	Within 2 weeks of study enrollment
Eligibility and Entry Characteristics, including baseline H&P and Zubrod PS	Within 2 weeks of study enrollment
Pathology Report	Within 2 weeks of study enrollment
Follow-up H&P data	At post XRT follow-up at 1, 3, 6, 9, and 12 months, then q 4 months year 2, then q6 months years 3-5; then annually
Tumor response evaluation	At post XRT follow-up at 3, 6, 9, and 12 months, then q 4 months year 2, then q6 months years 3-5; then annually
Adverse Event assessment	After each weekly treatment visit, then post XRT follow-up at 1, 3, 6, 9, and 12 months, then q 4 months year 2, then q6 months years 3-5; then annually
Healthcare Utilization/Cost Worksheet (Appendix VI),	Within 2 weeks of study enrollment, at the end of treatment, and at post treatment follow up at 1, 3, 6, 9, and 12 months, then q 4 months year 2, then q6 months years 3-5; then annually until death
FACT-L (Appendix VIII), EQ-5D (Appendix IX)	Within 2 weeks of study enrollment, at the end of treatment, and at post treatment follow up at 6 and 12 months,
Patient Perspective Cost Assessment (Appendix VII)	Upon radiation completion or first possible post treatment follow up (1 month). To be administered just once.

Data collection for QA

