11.1.2.4 Toxicity: Grade 3-5 adverse events as graded by CTCAE v 4.0

11.2 Sample Size Determination

The sample size calculation is based on the primary endpoint, overall survival at 1 year, and the assumption that patients are randomized until the end of accrual. The sample size is calculated with the 2-sided significance level of 0.05 and 80% statistical power using a 2-sample log rank test. We assume that the overall survival function follows an exponential distribution for each arm. Accrual to the study is assumed to be uniformly distributed. The null hypothesis is that the there are no difference in 1-year survival rates between two arms. We assume that the patients will be accrued for 2 years with a 1-year follow-up. We hypothesize that the patients randomly assigned to the control arm and experimental arm have a 1-year survival rate of 45% (hazard rate [λc]) of 0.799) and 60% (hazard rate [λe]) of 0.511), respectively, which is translated to the hazard ratio of $\lambda e/\lambda c = 0.640$. One interim analysis and a final analysis are planned for early stopping for efficacy. The efficacy testing is based on the Lan-DeMets spending function, which resembles the O'Brien-Fleming boundary. The total sample size of 226 patients (113 in the control arm and 113 in the experimental arm) will be accrued to achieve the desired 80% statistical power and 2-sided significance level of 0.05. Guarding against ineligibility or lack-ofdata rate of up to 5%, the final targeted accrual for this study will be 238 patients (119 per arm). Sample size was estimated using the sample size software EaST version 5.

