11.5.7 Toxicity

Any subject who receives treatment on this protocol will be evaluable for toxicity. Each patient will be assessed for the development of toxicity according to the Time and Events table (Appendix II). Toxicity will be assessed according to the NCI Common Toxicity Criteria for Adverse Events (CTCAE), version 4.0. Dose adjustments should be made according to the system showing the greatest degree of toxicity.

Only adverse events assessed to be definitely, probably, or possibly related to protocol treatment will be considered. The rates of all Grade 3-5 adverse events, and death during or within 30 days of discontinuation of protocol treatment will be tested for equality using a two-sided chi-square test with a 0.05 significance level.

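### Grade 3-5 toxicity is compared only as a crude pooled proportion, which cannot separate late risk per time alive from a survival difference; the expected distortion is modest

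*Combined protocol and SAP*

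**What the plan says.** The toxicity endpoint in section 11.1.2.4 is "Toxicity: Grade 3-5 adverse events as graded by CTCAE v 4.0", with no split between acute and late events. Section 11.5.7 sets the denominator: "Any subject who receives treatment on this protocol will be evaluable for toxicity". It then restricts the events: "Only adverse events assessed to be definitely, probably, or possibly related to protocol treatment will be considered". The rates of all such events, and of death during treatment or within 30 days of stopping it, "will be tested for equality using a two-sided chi-square test with a 0.05 significance level". A chi-square test of equality on these data compares the proportion of patients affected in each arm.

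Section 6.9 defines two periods. Events "from the signing of the informed consent, through 30 days post treatment will be considered acute adverse events"; those "from the end of acute monitoring, to 2 years post treatment, will be defined as late adverse events". Section 10.0, however, schedules adverse-event assessment at 1, 3, 6, 9 and 12 months, "then q 4 months year 2, then q6 months years 3-5; then annually", and Appendix II agrees. Section 11.5.7 refers to Appendix II and does not say at what time the test stops counting.

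For survival, section 11.2 assumes exponential distributions in which control patients "have a 1-year survival rate of 45" per cent, against 60 per cent in the experimental arm. Kaplan-Meier, log-rank and Cox methods are planned for overall survival, progression-free survival and time to local progression (sections 11.5.1 and 11.5.6), but not for toxicity.

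**The concern.** A patient who dies early can no longer have a late event. If Arm A lives longer, as the trial is powered to show, its patients spend more time at risk, and a larger share of them will have a late Grade 3-5 event even when the risk per year alive is the same in both arms. The reverse matters more for safety: if Arm A survived less well, its crude proportion would be held down and a real excess of late injury could be missed.

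Comparing toxicity is a named secondary objective (section 2.2.1), and section 9.9 raises the possibility that hypofractionation increases normal-tissue toxicity. Late severe injury is therefore something this comparison will be asked about.

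**Working it through.** **Inputs from the plan.** Hazards 0.799 (Arm B) and 0.511 (Arm A) per year, exponential survival, and 113 per arm (section 11.2); late period to 2 years post treatment (section 6.9); 60-month accrual (section 11.3) with 1-year follow-up (section 11.2), giving 1-6 years of observation.

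**Assumptions.** The documents give no late toxicity rate. I take an equal constant hazard h in both arms of 0.05, 0.10 or 0.20 per year alive. Where acute events are included, the acute risk q is equal in both arms, 20% by default. The clock starts at time zero for both arms, ignoring the different lengths of the treatment courses.

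**The plan's own figures first.** -ln(0.45) = 0.799, -ln(0.60) = 0.511, ratio 0.640. Schoenfeld's formula gives 158 events. Death probabilities under 2 years' accrual plus 1 year are 0.775 and 0.624, mean 0.700, so N = 158/0.700 = 226. The survival gap used here is the one on which the trial was sized.

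**Time at risk within 2 years.** Mean time alive = (1 - exp(-2λ))/λ.
- Arm A: (1 - 0.360)/0.511 = 1.25 years
- Arm B: (1 - 0.2025)/0.799 = 1.00 years
- Ratio 1.25

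**Late-event proportion.** With death as a competing event, p = h/(h+λ) × (1 - exp(-(h+λ)W)), W = 2. For h = 0.10 in Arm A: 0.10/0.611 × (1 - exp(-1.222)) = 0.115. The rejection probability is the normal approximation to the uncorrected chi-square test with 113 per arm.

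| h per year | Arm A | Arm B | Late-only test rejects |
|---|---|---|---|
| 0.05 | 6.0% | 4.8% | 6.8% |
| 0.10 | 11.5% | 9.3% | 8.6% |
| 0.20 | 21.3% | 17.3% | 12.0% |

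**The test as planned pools acute events.** Replace p by q + (1 - q)p with q = 0.20.

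| h per year | Pooled, 2-year cut-off | Pooled, 1-6 years' follow-up |
|---|---|---|
| 0.05 | 5.3% | 5.8% |
| 0.10 | 6.1% | 7.4% |
| 0.20 | 8.0% | 11.1% |

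At 2 years, q = 10% gives 5.6-9.4% and q = 30% gives 5.2-7.1%.

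**Shape of the late hazard.** If late risk is confined to the first 6 months (W = 0.5), the ratio of proportions is about 1.07 and even the late-only test rejects 5.1-5.3% of the time. Confined to 12 months, it rejects 5.4-6.5%.

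**Masking.** With the 2-year window and design hazards, a true rate of 0.079 per year in Arm A against 0.10 in Arm B gives equal crude proportions. By symmetry, if the survival hazards were reversed, an Arm A rate 0.10/0.079 = 1.27 times that of Arm B would look equal.

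**Check of the remedy.** In 10,000 simulated trials with equal hazards of 0.10, 0.20 and 0.30 and a 2-year window, a person-time comparison rejected 5.2%, 5.3% and 5.0% of the time, against 8.9%, 12.1% and 14.9% for the late-only crude test.

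**The case against.** A reader might infer that the planned test has an inflated type I error. The documents do not support that. The stated null is equality of rates, tested as proportions. When survival differs the cumulative proportions really do differ, and a rejection is then correct for that quantity. The share of treated patients who have a severe related event is a legitimate summary. Wanting the risk per year alive is a choice of a second question. This objection stands.

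A reader might also infer that events are counted for life, which would give late-only rejection rates of 9%, 13% and 19% over 1-6 years of follow-up. Those figures describe a test the plan does not contain. The planned test pools acute events, and section 6.9.2 expects a sizeable share of patients to have grade 3 esophagitis, which dilutes the late difference. The only defined late period ends at 2 years. Later visits are scheduled, so the cut-off is ambiguous rather than open-ended. Section 9.5 also ends follow-up at death or 5 years, although section 9.1 says until death.

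A constant hazard is also unfavourable to the plan. Section 6.9.3 places pneumonitis weeks to months after treatment, and section 6.9.1 places radiographic lung change mostly within six months. If late events behave likewise, little distortion remains.

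Finally, the effect needs a survival difference, no decision rule depends on this test, and the 30-day death comparison in the same sentence has a fixed post-treatment window. All of this limits the size. None of it supplies an analysis of late risk per time alive, and no other section does.

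**Conclusion.** The point holds as a modest limitation in what the toxicity comparison can answer, not as a broken test. Under the design's survival assumptions Arm A has about 25% more time at risk within 2 years. Equal late hazards of 0.05-0.20 per year then produce a gap of about 1 to 4 percentage points in late events. For the pooled test as planned, the chance of rejection is about 5-8% at 2 years and 6-11% over 1-6 years, given an equal 20% acute risk. These sizes rest on assumed late and acute risks and on a constant late hazard. They shrink to almost nothing with early-clustered late events, and there is no effect if survival is equal. The direction follows from the plan's own survival assumptions: a survival gain pushes Arm A toward looking more toxic, and a survival loss could conceal harm.

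**What to change.** In section 11.5.7:

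- Keep the chi-square comparison for acute Grade 3-5 related events in the fixed window to 30 days post treatment.
- State one cut-off for late events in the analysis, reconciling the 2-year definition in section 6.9 with the later assessments in section 10.0 and Appendix II.
- Add time to first late Grade 3-5 related event, compared by a cause-specific log-rank test and hazard ratio, with death as a censoring event.
- Describe late events by cumulative incidence with death as a competing event, noting that this curve still reflects the survival difference. The cause-specific comparison is what addresses risk per time alive.
- Report the crude proportion alongside.

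The cost is a second toxicity summary and a little programming. The schedules give assessment times and do not show that onset dates are recorded. If they are not, event timing is known only to the nearest visit, and the SAP should say how that is handled.

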11.4 Randomization Scheme

Patients will be allocated to the treatment using a randomized permuted block within strata to balance for patient factors other than institution. The stratifying variables are Zubrod performance status (2 vs. > 2) and stage (II vs. III).

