11.5.6 Progression-Free Survival (PFS) and Time to Local Progression

The time to disease progression and time to local regression will be estimated using the Kaplan-Meier approach. The stratified log-rank test will be used to test for a statistically significant difference in PFS and time to local progression distributions. The null and alternative hypotheses are H_0 : $S_1(t) < S_2(t)$ vs. H_A : $S_1(t) \ge S_2(t)$, where $S_i(t)$ is the distribution of survival times for patients in arm i. The Cox proportional hazard regression model will be used to determine hazard ratios and 95% confidence intervals for the treatment difference in progression-free survival and time to local progression. Unadjusted ratios and ratios adjusted for stratification variables and other covariates of interest will be computed.

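### Grade 3-5 toxicity and early death are compared with an unstratified chi-square test although randomization and the survival-type tests are stratified; a stratified test is an essentially free, usually small, improvement

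*Combined protocol and SAP*

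**What the plan says.** - **Randomization (11.4).** Allocation uses a "randomized permuted block within strata" scheme. On the factors: "The stratifying variables are Zubrod performance status (2 vs. > 2) and stage (II vs. III"). That makes four cells. The block size is not given.
- **Time-to-event tests (11.5.1, 11.5.6).** Overall survival is compared with a stratified log-rank test. For the other two endpoints: "The stratified log-rank test will be used to test for a statistically significant difference in PFS and time to local progression distributions".
- **Toxicity (11.5.7).** "Any subject who receives treatment on this protocol will be evaluable for toxicity". Only events at least possibly related to treatment count. The rates of Grade 3-5 events, and of death during or within 30 days of discontinuing treatment, "will be tested for equality using a two-sided chi-square test with a 0.05 significance level". No strata are mentioned and no reason is given for treating this endpoint differently.
- **Status of the endpoint.** Toxicity is a secondary objective (2.2.1) and a secondary endpoint (11.1.2.4). No power is stated for it.

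**The concern.** Stratified randomization makes the arms nearly equal in their mix of Zubrod status and stage. If event rates differ between strata, the pooled chi-square still counts the between-stratum variation in its variance, although the design has removed it from the treatment comparison. The variance is then too large and the test rejects less often than its nominal level allows.

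This is the only formal toxicity comparison in section 11. For a safety comparison, the cost of a conservative test is a somewhat greater chance of missing a real excess of severe toxicity or early death in one arm.

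**Working it through.** **1. The plan's own figure.** The plan states no sample size or power for toxicity, so the survival calculation in 11.2 is reproduced to fix N. It specifies a "2-sided significance level of 0.05 and 80% statistical power using a 2-sample log rank test".
- Hazards: −ln 0.45 = 0.799 and −ln 0.60 = 0.511; ratio 0.640.
- Events (Schoenfeld): 4(1.960 + 0.842)² / (ln 0.640)², which gives 158 after rounding up.
- Event probability with accrual A = 2 and follow-up F = 1 years: 1 − [e^(−λF) − e^(−λ(A+F))]/(λA) = 0.775 (control) and 0.624 (experimental); mean 0.6997.
- N = 158/0.6997 = 225.8, against 226 stated. Then 226/0.95 gives 238, as stated.

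**2. Level of the pooled chi-square under stratified randomization.** Let w be the stratum shares, p the stratum event rates and p̄ the overall rate.
- R = Σ w(p − p̄)² / [p̄(1 − p̄)], the share of outcome variance explained by the strata.
- Large-sample level = 2[1 − Φ(1.96/√(1 − R))].

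With R = 0 the level is 0.05. For it to fall to 0.045, R must reach about 0.044. With two equal strata, that means about 2% vs 13% at an overall rate of 7.7%, or about 20% vs 40% at an overall rate of 30%.

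Worked example, 20% vs 40% in equal strata: R = 0.10²/(0.30 × 0.70) = 0.0476, so the level is 2[1 − Φ(1.96/0.976)] = 0.045.

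**3. Rates in the documents.** Section 1.2 reports 4 of 52 patients with Grade 3 or higher treatment-related toxicity (7.7%). The dose-level counts there sum to 18 + 23 + 21 = 62, which would give 6.5%. No rates or shares by stratum are given, so those below are assumptions.

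**4. Simulation.** N = 226, permuted blocks of 4 (assumed), 100,000 to 300,000 trials per setting. Pearson chi-square is compared with Cochran-Mantel-Haenszel (CMH) without continuity correction. Power is at a common odds ratio of 2.3 (assumed).

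| Assumed stratum rates | Level, chi-square / CMH | Power %, chi-square / CMH |
|---|---|---|
| 10% in all strata | 0.051 / 0.050 | 59.7 / 58.9 |
| 20% in all strata | 0.050 / 0.050 | 79.6 / 79.4 |
| 4.3, 8.6% (mean 6.5%) | 0.050 / 0.049 | 43.8 / 43.7 |
| 5.1, 10.3% (mean 7.7%) | 0.051 / 0.050 | 49.6 / 49.4 |
| 3, 8, 4, 12% (early-death-like) | 0.047 / 0.048 | 39.1 / 39.8 |
| 13, 27% (mean 20%) | 0.0475 / 0.050 | 76.9 / 77.7 |
| 20, 40% (mean 30%) | 0.045 / 0.050 | 82.3 / 83.7 |
| 10, 30, 20, 50% | 0.038 / 0.049 | 75.4 / 79.5 |
| 5, 30, 30, 60% | 0.031 / 0.050 | 69.6 / 77.3 |

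**5. A second set of assumptions.** Here there are 113 per arm with exact balance, stratum shares of 45/20/25/10% and an odds ratio of 2.5.
- Rates 8/20/10/30% (nearly four-fold): level 4.6% vs 4.9%; power 72% vs 74%.
- The same gradient rescaled to an overall 7.7%: level 5.0% vs 5.1%; power 56.9% vs 57.3%.
- Overall 7.7% with no gradient: power 60.4% vs 59.5%.
- Rates 5/35/10/45% (nine-fold): level 3.3% vs 5.0%; power 64% vs 72%.

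**The case against.** A reader might infer that the planned test simply runs below 0.05 and gives up power. The documents do not support that. It would require Zubrod status or stage to predict treatment-related toxicity or early death, and nowhere do they say so or give rates by stratum. At the one Grade 3 or higher rate reported from effectively the same population, the two tests perform alike, and the 8-point loss needs a nine-fold gradient. This part of the objection stands, and the point has to be conditional.

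It also stands that the chi-square is valid. Any departure caused by stratified randomization is in the conservative direction, so false positives are not inflated beyond small-count discreteness. Nor does patient safety rest on this p-value: the monitoring committee reviews serious events as they are reported and adverse events quarterly (12.4), and all deaths enter the primary endpoint, which is tested with stratification.

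Two parts are weaker.
- **The 7.7% rate is not a ceiling.** Section 1.2 also cites a series with 7% Grade III acute esophageal and 6% Grade III or greater late pulmonary toxicity, and a 30-patient trial with four Grade 3 events (13% if in different patients). Section 6.9.2 expects Grade 3 esophagitis in a sizeable share of patients, and section 7.0 allows concurrent chemotherapy in the standard arm. Higher rates are therefore plausible, though that does not establish a gradient across strata.
- **The stratum definitions are incomplete, but that is not specific to this change.** Sections 3.1.2 and 3.1.4 admit recurrent disease and Zubrod 0-1 patients, who have no level in 11.4. The planned stratified log-rank tests need the same gap closed. Sparse cells are not a practical obstacle either: in the early-death-like setting CMH holds a level of 0.048.

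**Conclusion.** The inconsistency is real: one comparison ignores strata that the randomization and the time-to-event tests use. Its consequence is conditional and mostly small. The power given up is about nil at a 7.7% event rate, about 1 to 2 points at higher rates with two- to four-fold risk differences between strata, and 4 to 8 points only with very strong gradients. These figures rest on assumed stratum rates and shares, an assumed block size in the main simulation, and odds ratios of 2.3 or 2.5. It would be wrong to read this as an invalid test or a biased safety conclusion. The primary analysis and the sample size are unaffected. This is an optional improvement, worth making because it costs almost nothing.

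**What to change.** In 11.5.7, replace the chi-square test with a two-sided Cochran-Mantel-Haenszel test at 0.05 for both the Grade 3-5 rate and early death, stratified by the same strata as the log-rank tests. State that Zubrod 0-1 and recurrent patients are assigned to strata as for those tests.

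The cost is one sentence, plus an assignment rule that the log-rank analyses need in any case. No new data are required. If the strata are not prognostic, the loss is under 1 power point (59.7% vs 58.9%, or 60.4% vs 59.5%, in the settings above). The change should be made before outcome data are compared by arm.
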